Do trust in the healthcare system and/or health literacy impact engagement in a screening mammography program in the local Hispanic population? *We hypothesize that higher levels of trust and health literacy are positively related to engagement in a screening mammography program.*

Does a PN improve Hispanic women’s measures of trust in the healthcare system and satisfaction with communication in the screening mammography setting when compared to those receiving standard of care? *We hypothesize that women with access to a PN will have higher levels of trust in the healthcare system and satisfaction with communication than women receiving the standard of care.*

Methods:

*Study Design:* The study design is a randomized control trial. In this pilot study, 100 participants will be randomized to either a) the intervention, in which they receive care from the PN or b) the control, in which they receive the standard of care.

*PN Identification and Education:*

A PN will be identified and trained by [name], VICC Community Health Educator. [name] will supplement educational materials.

*Inclusion/Exclusion Criteria:*

Inclusion criteria will be Hispanic women meeting United States Preventive Services (USPSTF) criteria for screening mammography and criteria for clinical service coverage through the TN Breast and Cervical Cancer Screening Program.

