**Exclusion Criteria:**

- Personal history of breast cancer
- Current breast symptoms (palpable mass)

*Recruitment:*

We aim to recruit 100 women total. All participants will be informed that well woman screening is free under the TN Breast and Cervical Cancer Screening Program. Participants will be offered \$40 gift cards for compensation for participation. Two recruitment methods will be used.:

[figure not shown]
1. The research team will identify and recruit women meeting inclusion criteria from the MWCHC electronic medical record. Eligible participants identified from the MWCHC will be contacted via telephone. **[See recruitment material]**.
2. The research team will identify and recruit women from the local Hispanic community through churches, community organizations, and community events. We will also use radio announcements and Facebook for recruitment **[See recruitment material]**.

At the time of recruitment, women will be assisted in scheduling an appointment at MWCHC for well woman screening during a “Hispanic Clinic Day”.

*Hispanic Clinic Days:*

Women will be scheduled during one of five dedicated “Hispanic Clinic Days”. Each clinic day will host up to 20 women, to a target 100 participants. Each day there will be a morning session for 10 women and an afternoon session for 10 women. The bilingual research assistant and bilingual PN will be present during the Hispanic Clinic Days. At the start of each session, consent will be obtained from all potential participants, followed by baseline assessments, randomization and clinical care. Gift cards will be distributed at time of written consent.

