All participants will be contacted via telephone by the bilingual research assistant 2 -5 days after results are distributed by standard method for post assessment. This will be conducted in English or Spanish according to participant preference. This post assessment will repeat the measures of trust. It will also assess measures of satisfaction with care, satisfaction with communication, relationship with the promotora and intent to follow-up [**see attached post assessment**]. After the post

assessment, the existing Vanderbilt Ingram Cancer Center (VICC) Breast and Cervical Cancer pamphlet [**see attached VICC Breast and Cervical Cancer pamphlet**].

*Delayed Chart Review:*

The bilingual research assistant will perform delayed chart review 2-4 weeks following delivery of results to assess whether patients needing follow-up diagnostic studies returned. Delayed chart review may also occur in 2-3 years to assess adherence to continued screening.

*Data Collection:*

Baseline assessment data will be collected by paper and pencil (in Spanish or English language per patient request) immediately following consent at MWCHC. The bilingual research assistant will be available to assist as necessary. Post assessment data will be collected electronically in REDCap by bilingual research assistant via telephone. Return for Follow-Up data will be accessed via patient medical record. Data will be stored in a REDCap.

*Item Development:*

**Baseline Assessment:** The baseline assessment will collect demographic information. Additionally, the baseline assessment will assess trust in the healthcare system using the Healthcare System Distrust Scale and health literacy using the Self-Reported Health Literacy Scale.

**Post Assessment:** Measures of healthcare system distrust will be repeated in the post assessment. The post assessment will include multiple items to assess satisfaction with care using the Patient Satisfaction with Cancer Scale, satisfaction with communication adapted from the Interpersonal Processes of Care Survey, and satisfaction with the promotora. The post assessment will also assess intent to follow up.

*Statistical Considerations:*

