Descriptive statistics will be used to analyze the demographic characteristics of participants. Comparison of knowledge in baseline and post assessments will be assessed with  $\chi^2$ , Student *t* tests and Fischer exact tests as necessary. Open-ended responses will be analyzed qualitatively. Post assessment comparison between “intervention” and “control” groups will be assessed with  $\chi^2$ , Student *t* tests and Fischer exact tests as necessary. Open-ended responses will be analyzed qualitatively.

*Sample Size:*

For this pilot study, the proposed sample size of 50 patients/group provides at least 80% power to detect a 29% improvement of the success rate, i.e. 40% vs 69%, with 2 sided Type 1 error = 5%. This calculation was based on the Chi squared test with the normal approximation correction for continuity.

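### The stated 80% power is what the design gives at its enrolment ceiling, with essentially no reserve and no allowance for no-shows, refusals or missed telephone calls

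*Combined protocol and SAP*

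**What the plan says.** All references are to the Combined protocol and SAP.

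- **Sample Size** (under Statistical Considerations): "the proposed sample size of 50 patients/group provides at least 80% power" for a difference of 29 percentage points, namely 40% versus 69%, "with 2 sided Type 1 error = 5" percent. On method: "This calculation was based on the Chi squared test with the normal approximation correction for continuity". No adjustment for loss appears.
- **Study Design**: "100 participants will be randomized to either a) the intervention, in which they receive care from the PN or b) the control". The sizing is therefore for two groups.
- **Hispanic Clinic Days**: "Women will be scheduled during one of five dedicated" sessions, and "Each clinic day will host up to 20 women, to a target 100 participants". Consent is taken at the start of each session, after slots have been booked.
- **Post Assessment**: women are telephoned "2 -5 days after results are distributed by standard method for post assessment". The call collects satisfaction with care, satisfaction with communication, relationship with the promotora and intent to follow up, and it repeats the trust measure. Statistical Considerations compares intervention with control on this assessment.
- **Delayed Chart Review**: return for follow-up is taken from the medical record, among women who need further diagnostic studies.

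No section gives an expected loss rate, replacement of participants, over-booking, extra clinic days or a way of handling missing data.

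**The concern.** Power depends on the number analysed, not the number of slots. Here the number assumed in the calculation, the recruitment target and the clinic capacity are all 100. A woman who misses her session or declines consent leaves an empty slot, and one who cannot be reached by telephone contributes nothing to the post-assessment comparison. Losses can only lower the number analysed, and nothing in the plan offsets them.

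Wording the power as a minimum therefore gives the wrong impression: about 80% is close to the most this design can deliver for that contrast. A reader of a null between-arm result could credit it with more sensitivity than the trial had.

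**Working it through.** **Inputs.** From Sample Size: p1 = 0.40, p2 = 0.69, difference d = 0.29, two-sided alpha 0.05 (z = 1.96), n = 50 per group, continuity correction. From Hispanic Clinic Days: 5 days × up to 20 women = 100 at most. Loss rates of 10% and 20% are assumptions.

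**Formulas.** For n per group, the continuity correction is c = 1/n. The standard error under no difference is s0 = √[2·p̄(1−p̄)/n] with p̄ = 0.545. The standard error under the alternative is s1 = √[(p1(1−p1) + p2(1−p2))/n].

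- Pooled: power = Φ[(d − c − 1.96·s0)/s1]
- Unpooled: power = Φ[(d − c)/s1 − 1.96]
- Exact: sum the binomial probabilities of all tables in which the continuity-corrected chi-squared exceeds 3.841

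**Reproducing the plan's figure, n = 50.** s0 = 0.0996, s1 = 0.0953, c = 0.02.

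- Pooled: (0.29 − 0.02 − 0.1952)/0.0953 = 0.785, power 78.4%
- Unpooled: 0.27/0.0953 − 1.96 = 0.874, power 80.9%
- Exact: 80.03%

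The stated 80% is therefore reproduced within rounding of method. As a cross-check, the usual sample-size formula gives 45.1 per group uncorrected. With the correction it gives (45.1/4)·[1 + √(1 + 4/(45.1 × 0.29))]² = 51.8, so 52 per group, just above the planned 50.

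**Power when fewer are analysed (continuity-corrected, 40% versus 69%).**

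| Analysed per group | Pooled | Unpooled | Exact |
|---|---|---|---|
| 50 | 78.4% | 80.9% | 80.0% |
| 49 | 77.4% | 80.0% | 78.5% |
| 48 | 76.4% | 79.0% | 77.0% |
| 45 (10% loss) | 73.2% | 76.0% | 71.9% |
| 40 (20% loss) | 67.0% | 70.1% | 69.2% |

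**Could enrolment absorb the loss?** Keeping 50 analysed per group needs 50/(1 − loss): 53 at 5%, 56 at 10% and 63 at 20%. That is 106, 112 and 126 women in total, all above the capacity of 100.

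**Effect of the arm structure.** The Randomization paragraph assigns women to a control arm and two intervention arms. If allocation is equal (the ratio is not stated) and the two promotora arms are pooled, the comparison is 33 versus 67. Continuity-corrected power is then about 73–74% with no loss at all. This is a separate inconsistency, but it means the table above applies only to two equal groups.

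**The case against.** **The calculation is not wrong.** A reader might infer an arithmetic error. The documents do not support that: the claim is conditional on 50 per group, and at 50 analysed it reproduces. The fault is the missing allowance.

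**Not every single loss breaks 80%.** It is tempting to say that any loss takes power below the stated figure, or that the figure holds only with complete attendance, consent and contact. That depends on the method. Unpooled, losing one woman from one group leaves 80.4–80.5%. Pooled, power is already 78.4% with nobody lost. What stands is that all three methods are below 80% by 48 per group.

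**The margin depends on the correction.** Without it, the normal approximation gives 84.0% at 50 per group, 80.8% at 46 and 79.9% at 45. The plan says the correction was used for sizing, so that is the right standard for its claim, though it does not say the final chi-squared test will be corrected.

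**Not every between-arm outcome needs the call.** Return for follow-up comes from chart review, so it would be wrong to say that arm comparisons exist only for women reached by telephone. That outcome covers only women needing further studies, however, so it would not supply 50 per group either. The plan never says what the 40% versus 69% measures. Linking it to the telephone assessment is an inference, though it fits the two-group comparison described.

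**The stakes are modest.** The trial is labelled a pilot, and its listed primary outcome is the relationship between trust and engagement, which this power figure does not govern. Nor do the documents show that contact will be poor; the call is made soon after results and in the woman's preferred language. All of this stands. It limits the consequence but does not make the minimum-power wording accurate.

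**Conclusion.** The point holds as a missing allowance, not as a miscalculation. The stated 80% is power at the enrolment ceiling: 78–81% with 50 analysed per group, below 80% by every continuity-corrected method at 48, about 72–76% at 45 and about 67–70% at 40. The direction is certain, because capacity prevents any compensating enrolment. The size rests on assumed losses of 10% and 20%, on two equal groups, on the continuity correction the plan names, and on the success rate being a post-assessment outcome. If the success rate is something else, or the three-arm allocation stands, the figures change and must be recomputed for that contrast.

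**What to change.** Keep 100 women and revise the Sample Size paragraph in this order:

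1. Name the endpoint to which 40% versus 69% refers, and define success on it.
2. Reconcile the two-group sizing in Study Design and Sample Size with the three arms in Randomization, and state the allocation and the contrast being powered.
3. Replace the minimum-80% wording with the power for that contrast at the number expected to be analysed, and state the assumed rate of non-attendance, refusal and non-contact.

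If two equal groups are retained, the sentence could say that 100 women will be enrolled and that, assuming 10–20% are not available for analysis, 40–45 per group give about 67–76% power for 40% versus 69%. This example should not be adopted while the three-arm text stands.

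The cost is a short text revision and a less favourable stated power. It needs no extra patients or clinic days.

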**Anticipated Outcomes:**

*Primary Outcome:*

Assess relationship between trust in healthcare system and engagement in screening mammography program in local Hispanic women.

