**Secondary Outcome:**

Assessment of PN impact on Hispanic women’s measures of satisfaction with communication when compared to those receiving standard of care treatment in the screening mammography setting.

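### The plan's only power figure (80% for 40% v 69%) names no endpoint: it is not the power for the primary trust-engagement association, and it is not tied to the communication measure

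*Combined protocol and SAP*

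**What the plan says.** All references are to the combined protocol and SAP.

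- **Sample Size** gives 50 patients per group and at least 80% power for "a 29% improvement of the success rate, i.e. 40% vs 69%, with 2 sided Type 1 error = 5" per cent, using a chi-squared test with continuity correction. It names no endpoint, instrument or cut-off and gives no source for 40% or 69%. The supplied text does not define success anywhere else.
- **Primary Outcome**: "Assess relationship between trust in healthcare system and engagement in screening mammography program in local Hispanic women".
- **Secondary Outcome**: the navigator's effect on "measures of satisfaction with communication when compared to those receiving standard of care treatment".
- **Item Development** describes "satisfaction with communication adapted from the Interpersonal Processes of Care Survey". On trust, "Measures of healthcare system distrust will be repeated in the post assessment", and the same distrust scale is collected at baseline. It adds: "The post assessment will also assess intent to follow up".
- **Statistical Considerations** lists chi-squared, t and Fisher tests, to be used as needed, for the comparison of intervention with control. It assigns none of them to a named outcome.
- **Study Design** describes two groups. **Randomization** describes a control arm and two navigator arms (individual and group education) and gives no ratio.

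**The concern.** A power statement describes one test of one endpoint, and here the endpoint cannot be identified. The primary outcome is a relationship among participants, not a comparison of two randomised groups of 50. The secondary outcome comes from a survey measure for which the text gives no threshold. Intent to follow up, or later screening adherence, could yield a proportion, but the paragraph refers to neither.

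A reader therefore cannot tell what difference in communication or distrust 100 women could show, and nothing is said about the precision of the primary association. Unless the unsupplied survey documents fix a scoring rule, both the test and any cut-off could be settled after the data are seen. The two-group calculation also does not fit the three-arm randomisation.

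**Working it through.** **1. The plan's own figure.** Inputs from Sample Size: p1 = 0.40, p2 = 0.69, n = 50 per group, two-sided alpha 0.05, continuity correction.

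- Corrected difference: 0.29 − ½(1/50 + 1/50) = 0.27.
- Pooled rate 0.545, so the null SE = √(0.545 × 0.455 × 2/50) = 0.0996.
- SE under the alternative = √[(0.40 × 0.60 + 0.69 × 0.31)/50] = 0.0953.
- Power = Φ[(0.27 − 1.960 × 0.0996)/0.0953] = Φ(0.785) = 78.4%. The same approximation needs 52 per group for 80%.
- Exact binomial enumeration of the corrected test at 50 v 50 gives 80.0%.

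The stated figure is reproduced to an acceptable accuracy.

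**2. Three arms.** Assume equal three-way allocation and pooled navigator arms, so about 67 v 33. Exact enumeration of the same test and rates gives 74.2%.

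**3. Continuous scores between arms.** The standardised difference detectable with 80% power (noncentral t, two-sided 5%, complete follow-up, independent observations) is:

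| Groups | Unadjusted | Baseline-adjusted, r = 0.5 (assumed) |
|---|---|---|
| 50 v 50 | 0.566 SD | 0.566 × √(1 − 0.25) = 0.490 SD |
| 67 v 33 | 0.602 SD | 0.602 × √(1 − 0.25) = 0.521 SD |

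The adjusted column applies to distrust, which is measured at baseline and again after results. Communication is measured only afterwards.

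**4. Primary association.** For N = 100, the 95% CI half-width for the difference in mean distrust between engaged and non-engaged women is t(98) × √(1/n1 + 1/n2), with t(98) = 1.984. All splits are assumed.

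- 50/50: 1.984 × 0.200 = 0.40 SD
- 80/20: 1.984 × 0.250 = 0.50 SD
- 90/10: 1.984 × 0.333 = 0.66 SD

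An uneven split is plausible because enrolment takes place at the screening visit: "At the start of each session, consent will be obtained from all potential participants, followed by baseline assessments, randomization and clinical care".

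**5. What cutting a score would cost, if it were done.** Under normality (assumed), 40% v 69% is a shift of z(0.69) − z(0.40) = 0.496 + 0.253 = 0.749 SD. At 50 v 50 a t test then has 96.0% power. The uncorrected chi-squared test on the cut score has 85.3% and the corrected test 80.0%. So of the 16-point gap, about 11 points come from cutting the score and about 5 from the continuity correction. The corrected test's true size when both rates are 40% is about 3.2%, against 5.2% without the correction.

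**The case against.** The strongest reply is that this is a self-described pilot, that 100 equals the clinic capacity (five days of up to 20 women), and that the arithmetic works. All three are correct. They do not say what the 80% refers to, and the plan chose to claim it.

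A second reply is that the attached post assessment may hold a scoring rule. It may, and it could not be checked. The Sample Size paragraph points to no such rule, and a communication cut-off would still leave the primary association uncovered.

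A third is that t tests are already listed, so a continuous comparison is already possible. That stands: what is missing is the assignment of a test to each outcome, and the use of baseline distrust. Between-arm trust is a stated objective, though not one of the two named outcomes.

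A reader might infer that the plan gives up 16 points of power by cutting the communication score. The documents do not support this. Nowhere do they say that the score will be cut, and part of that gap comes from the continuity correction. Nor do they support the inference that 100 women are too few: no target difference is given for either named outcome.

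**Conclusion.** The concern holds in a limited form. The 80% belongs to an unnamed binary endpoint in two equal groups. It is not the power for the primary outcome, and nothing links it to the secondary one. The calculation is sound at 50 v 50. The fall to about 74% depends on equal three-way allocation and pooling, neither of which is stated, so it shows that the figure does not fit the randomisation described and is not a firm estimate of the trial's power.

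The detectable differences assume complete follow-up and independent observations. Women attend in sessions of 10 and one arm is taught in groups, so clustering could make them optimistic. The gain from baseline adjustment depends on the assumed correlation of 0.5. The half-widths for the primary association depend on a definition and a split of engagement that the plan does not give, so they are illustrations only.

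**What to change.** 1. State that communication and distrust are compared between arms as continuous scores, with post-assessment distrust adjusted for its baseline value. The baseline value is already collected, so this needs no new data.
2. Replace the 80% with the detectable difference at 80% power: about 0.57 SD at 50 v 50, or 0.60 SD at 67 v 33 if three equal arms are pooled. State the assumptions of complete follow-up and independence, and reconcile the two-group and three-arm descriptions so that one figure applies. Alternatively, keep 40% v 69% only for a named binary measure, such as intent to follow up, with its cut-off fixed in advance.
3. Say that this power does not cover the primary association. Define engagement and give the precision for a range of splits, such as the 0.40 to 0.66 SD above.

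The cost is one rewritten paragraph and a less simple headline figure; enrolment does not change. If engagement is to be defined by later screening, note that this review is only optional at present: "Delayed chart review may also occur in 2-3 years to assess adherence to continued screening". The definition would then rest on data that the plan does not commit to collecting.

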**HISPANIC CLINIC DAY FLOW CHART**

*Consent:*

Written informed consent will be obtained for all participants by the research assistant in person at MWCHC [**see attached consent**].

*Baseline Assessment:*

Immediately following consent, all participants will complete a baseline assessment (English or Spanish according to participant preference) to collect demographic information, trust in healthcare system assessment, and health literacy assessment [**see baseline survey**]. This assessment will be collected by paper and pencil with the help of the research assistant.

*Randomization:*

Women will be randomized to the control arm, the intervention arm 1 (individual education), or the intervention arm 2 (group education) immediately following consent. Randomization will be performed using the random number generator software available in the R statistical package ([www.r-project.org](http://www.r-project.org)).

*Control Arm:*

Immediately following consent and completion of the baseline assessment, women in the control arm will receive standard of care well woman screening. The control arm will receive screening results per MWCHC protocol.

*Intervention Arm 1:*

Immediately following consent and completion of the baseline assessment, women in the intervention arm 1 will participate in a 20-30 minute educational session [**see educational slides**] alone with the PN. Well woman screening will follow the educational session. The PN will be available to assist with questions and language interpretation as necessary. After standard delivery of screening results, the PN will contact these participants to answer any questions about their screening results and to assist with scheduling any additional tests necessary.

*Intervention Arm 2:*

Immediately following consent and completion of the baseline assessment, women in the intervention arm will participate in a 20-30 minute group educational session [**see educational slides**] from the PN. Well woman screening will follow the educational session. The PN will be available to assist with questions and language interpretation as necessary. After standard delivery of screening results, the PN will contact these participants to answer any questions about their screening results and to assist with scheduling any additional tests necessary.

*Post Assessment 2-5 Days After Delivery of Results:*

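### Efficiency point: naming Boschloo's exact test in advance for two-group proportions holds the 5% limit and gains some power over Fisher or corrected chi-squared (80.0% to 82.7% at 50 v 50)

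*Combined protocol and SAP*

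**What the plan says.** The Sample Size paragraph under Statistical Considerations states that "the proposed sample size of 50 patients/group" "provides at least 80% power to detect a 29% improvement of the success rate", namely from 40% to 69%, with a two-sided type 1 error of 5%. On the method it says: "This calculation was based on the Chi squared test with the normal approximation correction for continuity".

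The analysis paragraph just above it lists chi-squared, Student t and "Fischer exact tests as necessary" for comparing the intervention and control groups at the post assessment. It does not say whether the chi-squared test will be continuity-corrected, and it gives no rule for choosing between chi-squared and Fisher. No unconditional exact test is mentioned.

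The design text is not consistent on the number of groups. Study Design and Sample Size describe two, but the Randomization paragraph says: "Women will be randomized to the control arm, the intervention arm 1 (individual education), or the intervention arm 2 (group education) immediately following consent".

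**The concern.** A 5% test on a 2 x 2 table rarely has a true error of exactly 5%, because only finitely many tables can occur. Fisher's test and the continuity-corrected chi-squared test err on the safe side, sometimes by a lot, and the unused error costs power. The uncorrected chi-squared test can err the other way.

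This matters here for two reasons. The planned power sits at 80% with nothing in hand: enrolment is set at five clinic days of up to 20 women, the outcome is collected later by telephone, and no allowance is made for loss. Also, leaving the test open until the data are seen leaves open a maximum error anywhere between 3.5% and 5.7% at 50 v 50.

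**Working it through.** **Inputs.** From the Sample Size paragraph: 50 per group, success rates 0.40 and 0.69, two-sided 5%, continuity-corrected chi-squared. From the analysis paragraph: chi-squared (correction not stated) or Fisher. No dropout rate is given, so none is used.

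**Reproducing the plan's figure.** By the normal approximation with the correction, the pooled rate is (0.40 + 0.69)/2 = 0.545.
- Null standard error: √(2 × 0.545 × 0.455/50) = 0.0996, and 1.96 × 0.0996 = 0.1952.
- Standard error under the alternative: √((0.40 × 0.60 + 0.69 × 0.31)/50) = 0.0953.
- z = (0.29 − 1/50 − 0.1952)/0.0953 = 0.785, so power is 78.4%. The matching sample-size formula gives 52 per group.
- Without the correction, z = (0.29 − 0.1952)/0.0953 = 0.995, so power is 84.0%.

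The corrected approximation is within 2 points and 2 patients of the plan. The exact calculation below gives 80.03%, so the stated power holds.

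**Exact error and power.** With x successes of n1 and y of n2, each test rejects a fixed set R of tables. Writing b for the binomial probability:
- error at a common rate p = Σ over R of b(x; n1, p) · b(y; n2, p), maximised over a grid of 1,999 values of p;
- power = Σ over R of b(x; n1, 0.40) · b(y; n2, 0.69).

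Boschloo's test rejects when Fisher's p-value is at or below a cut-off, set as high as possible with the maximum error still at or below 5%. At 50 v 50 that cut-off is about 0.0693. Results over the 51 × 51 = 2,601 tables:

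| Test at 50 v 50 | Maximum true error | Power, 40% v 69% |
|---|---|---|
| Corrected chi-squared | 3.52% | 80.0% |
| Fisher | 3.52% | 80.0% |
| Boschloo | 4.87% | 82.7% |
| Uncorrected chi-squared | 5.69% | 85.3% |

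The first two tests reject exactly the same 1,740 tables; their error is 3.21% at a common rate of 40%. Boschloo rejects all of these and 1,796 − 1,740 = 56 more. It first reaches 80% power at 46 per group (80.1%); the corrected and Fisher tests first reach it at 50.

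**Other splits.** The first number is the group with the 40% rate. The splits are illustrations, since the documents state neither attrition nor an allocation ratio for three arms.

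| Split | Fisher, maximum error | Fisher power | Boschloo power | Gain, points |
|---|---|---|---|---|
| 50/50 | 3.5% | 80.0% | 82.7% | 2.7 |
| 49/50 | 4.4% | 82.4% | 82.6% | 0.2 |
| 49/51 | 4.6% | 81.4% | 81.7% | 0.4 |
| 45/45 | 3.2% | 72.3% | 78.7% | 6.3 |
| 34/66 | 4.0% | 77.0% | 79.3% | 2.2 |
| 33/33 | 3.6% | 61.3% | 63.6% | 2.2 |

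Gains are taken before rounding. The corrected chi-squared test stays conservative: its maximum error is 3.5% at 49/51 and 2.9% at both 45/45 and 34/66, with power 80.6%, 71.9% and 73.5%. In every split checked, Boschloo rejected each table that Fisher or the corrected test rejects.

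**The case against.** The strongest reply is that nothing in the plan is wrong. A reader might infer from a true error of 3.5% that the stated 5%, or the stated power, is false. The documents do not support that: 5% is an upper limit, which the corrected and Fisher tests respect, and at least 80% power is true for the test named. This objection stands in full.

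A reader might also infer that the trial is committed to a conservative test and so throws power away. The sentence about the continuity correction describes the sample-size calculation only. If the chi-squared analysis were uncorrected, power at 50 v 50 would be 85.3%, and moving to Boschloo would lower it by 85.3 − 82.7 = 2.6 points. That stands too, but the uncorrected test does not hold 5%, so it is not a like-for-like alternative.

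The 2.7-point gain belongs to an exact 50/50 split. Randomization by a random number generator, with no blocking described, and follow-up by telephone do not secure that split. One missing woman can almost remove the gain over Fisher; other splits enlarge it. The gain is therefore real but uneven. Even at 50/50, the rate detectable from 40% with 80% power moves only from 69.0% to 68.1%.

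Finally, the success rate in the power statement is tied to no named outcome, and trust and communication are measured by multi-item scales. Scores compared by t test are untouched by this change.

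**Conclusion.** This is an optional efficiency improvement, not an error. For intervention v control comparisons of proportions, Boschloo's test holds the error at or below 5% and loses no result that would be significant under Fisher or the corrected chi-squared test in the splits checked. At 50 v 50 and 40% v 69% it raises power from 80.0% to 82.7%, worth about 50 − 46 = 4 women per group. Elsewhere the gain over Fisher ran from 0.2 to about 6 points. Fixing one test in advance also closes the open choice between tests whose maximum error at 50 v 50 ranges from 3.5% to 5.7%.

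It would be tempting to read 83% as the trial's power. The documents do not support that yet: it assumes two groups with 50 analysed in each, while the Randomization paragraph describes three arms. If the arms were equal and the two intervention arms pooled (assumed 34 v 66), Boschloo gives about 79%; a comparison of two single arms of 33 gives about 64%. Reconciling the arms matters more than the choice of test.

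**What to change.** Before outcome data are seen, amend the analysis paragraph under Statistical Considerations to name Boschloo's exact unconditional test, two-sided at 5%, for intervention v control comparisons of proportions, in place of the open choice between chi-squared and Fisher. Leave the t tests for scale scores as they are. The change does not extend to baseline v post comparisons, which are made within the same women.

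Reconcile the number of randomized arms between Randomization, Study Design and Sample Size. Only then restate power: about 83% for 40% v 69% if there are two groups with 50 analysed in each, or a figure recomputed for the groups that will actually be compared.

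The cost is wording and a less familiar test, plus 2.6 points of power relative to an uncorrected chi-squared test that does not hold 5%. No extra participants, visits or data are needed.
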